**Procedures for Evaluating Proximal Implementation Outcomes:**

**Reach Outcome:** For this study outcome, Reach (i.e. the number of individuals who are willing to participate in an initiative) is defined as the absolute number of Black cis-gender women who receive a PrEP prescription. We will also evaluate the proportion of women prescribed PrEP who had a PrEP indication. PrEP indication will not be defined using the Center for Disease Control and Prevention (CDC) PrEP indication clinical guidelines due to evidence suggesting these criteria are too restrictive and may not predict risk. Instead we will define PrEP eligibility based on the CDC’s guidance summary criteria, deeming those PrEP eligible who meet any of the following criteria for cis-gender women not living with HIV (over a 6-month timeframe): HIV-positive sex partner, bacterial STI (gonorrhea or syphilis), more than one sex partner, inconsistent condom use, sex for exchange of goods, or being in a high-prevalence network. This data will be obtained based on the sexual risk screener (a component of implementation strategy) documented in the chart during patient visits.

**Procedures.** Data will be collected from the university’s electronic medical record, looking at visit data for all cis-gender women with clinic visits during the pilot timeframe. We will be able to extract prescription data directly, but PrEP eligibility and referral will require review of chart documentation.

**Preliminary Effectiveness Outcome:** To evaluate effectiveness of PrEP4Her, we will determine increases in PrEP prescriptions over-time. We will also evaluate what patient factors are associated with PrEP prescription.

**Procedures.** A data extraction of the UAB electronic medical record will be done (as described above) at 3-month time intervals after implementation of PrEP4Her (i.e. baseline, 3-months and 6-months’ time). We will collect the following patient demographics: age, race, ethnicity, and insurance status.

**Statistical analysis.** Frequencies for prescription will be reported overall and for each independent variable (i.e. patient demographics), at each of the 3 time points (baseline, 3 months and 6 months). Means, standard deviations and t-test comparisons between those referred and prescribed PrEP will be reported for continuous

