independent variables if normally distributed. For variables with excessive skewness or otherwise non-normal distribution, medians with upper and lower interquartile ranges will be reported compared by Wilcoxon rank sum test. Categorical independent variables will be reported as frequencies and percentages and compared by chi-square and Fisher's exact test. Bivariate models will be fit and variables with p-values  $\leq 0.1$  will be included in multivariable logistic regression analyses. Model fit will be determined using Hosmer and Lemeshow tests.

**Adoption Outcome:** As a dimension within the RE-AIM framework, we define adoption as the proportion of key-stakeholders within our pilot site who were willing to initiate our implementation strategy. In order to assess this, we will conduct and document the following procedures.

**Procedures.** Trainings: During synchronous trainings we will document the number of providers and staff who attend meeting. Asynchronous attendance will be captured through collecting para-data (to track clicks) on the number of providers and staff who visit the CFAR website and access training materials. Additionally, we will connect a REDCap survey link to the end of training materials that will include a single-item asking "Did you access these training materials to aid in PrEP implementation at the UAB GYN Continuity Clinic?". Sexual History: We will conduct a chart review (similar to what was described above), to evaluate absolute number of patients seen during our pilot timeframe who had a sexual history taken.

**Acceptability Outcome:** We are defining acceptability as the extent to which key stakeholders, both provider delivering the intervention and Black cis-gender women receiving it, felt PrEP4Her was acceptable. In order to assess this, we will conduct key-informant interviews with stakeholders.

**Sample.** Key informants will include 15-20 stakeholders from our pilot site (including approximately 10 providers, managers, and other support staff), as well as Black cis-gender women (approximately 10-15) who were seen during the 6-month intervention pilot.

**Recruitment.** We will recruit key stakeholders directly from our pilot site and Black cis-gender women will be recruited after the pilot through flyers and direct referral from clinical staff.

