### Objectives

(Primary manuscript) Mixed methods paper evaluates the implementation outcomes, using the RE-AIM framework, of the PrEP4Her intervention in a low barrier gynecology setting.

(Primary/Fidelity) Described fidelity to PrEP4Her from the end-user perspective. Describe results from survey, compare/contrast with EHR review (EHR data confirms the number of PrEP prescriptions)

**Study population:** Reproductive aged women 18-45 who received the PrEP4Her intervention as a component of their standard care from January 2023 – August 2024 [Pre-implementation stage Jan – July 2023; PrEP4Her implementation July 2023 January 2024; Pilot January 2024-August 2024].

**PreP4HER components** - Universal sexual history screener, synchronous PrEP training, job aides [pocket cards with CDC PrEP guidance and 5Ps, EHR documentation/order aids, educational materials, asynchronous training on communication strategies

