#### Quantitative data

1. Visits per period (of intervention) with number of PrEP prescriptions
  - a. Patient visits by intervention period; total n=4161
  - b. PrEP prescriptions per period; n=11
2. EHR review (to confirm PrEP prescriptions)
  - a. Total charts reviewed n= 4635; missing =6
3. Demographics of all patients
  - a. Race
  - b. Sex at birth assignment
  - c. Gender in EHR
  - d. Lab results
    - i. Chlamydia
    - ii. Gonorrhea

- iii. Syphilis
- iv. HIV

4. Demographics of patients with a PrEP prescription

- a. Race
- b. Sex assigned at birth
- c. Gender assigned in HER
- d. Lab results
  - i. Chlamydia
  - ii. Gonorrhea
  - iii. Syphilis
  - iv. HIV

5. Sexual health pre-screener survey; n=1135

- a. Sociodemographics
  - i. Race
  - ii. Sex assigned at birth
  - iii. Gender in EHR
  - iv. Lab results
    - 1. Chlamydia
    - 2. Gonorrhea
    - 3. Syphilis
    - 4. HIV
- b. Sexual health pre-screener outcomes; n=1135
  - i. Types of sexual behaviors
  - ii. Gender of partners
  - iii. Sexually active in last year
  - iv. Number of sexual partners in past year
- c. Data on when participants were seen (by month/year)

6. Post visit (fidelity) survey data; n=242

- a. Demographics
  - i. Race
  - ii. Education
  - iii. Employment
  - iv. Insurance
  - v. Estimated household income
  - vi. Reason for visit
  - vii. Anal sex in past 6 months
  - viii. Condom use history
  - ix. Number of partners
  - x. Gonorrhea or syphilis diagnosis, past 6 months
  - xi. Partner living with HIV and not on medication
  - xii. Did provider take sexual history?

- xiii. Saw educational materials during visit?
- xiv. Spoke with provider about PrEP?
- xv. Prescribed PrEP during visit?

- b. Fidelity items
  - i. Comfort discussing PrEP w/ provider
  - ii. Understood side effects of PrEP after discussion w/ provider
  - iii. Provider discussed how to pay for PrEP
  - iv. Felt confident could take PrEP daily after visit
- c. Row percentages -Talked to doctor about PrEP and demographics

7. PrEP prescriptions data with physician and intervention period

- a. Demographics of patient prescribed; n=11
  - i. Race
  - ii. Age
  - iii. Lab results
  - iv. Earliest Emtricitabine-Tenofovir
  - v. Study Prescription Date
  - vi. Order Date

8. Number of women with a PrEP indication seen during the study visit (no indication/STI in last 12 months/multiple partners/STI in last 12 months and multiple partners); n=4241

- a. Data by visit date

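### The only groups named for testing, referred versus prescribed, do not answer which factors are associated with PrEP prescription, and the SAP leaves open a screened multivariable model with 11 prescriptions

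*Combined protocol and SAP*

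**What the plan says.** **Protocol, Aim 3.** The preliminary effectiveness outcome includes an objective to learn which patient factors go with PrEP prescription.

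- Data source (Reach, Procedures): the medical record, "looking at visit data for all cis-gender women with clinic visits during the pilot timeframe". The same paragraph says "PrEP eligibility and referral will require review of chart documentation" and does not define referral further.
- Candidate factors (Preliminary Effectiveness, Procedures): "We will collect the following patient demographics: age, race, ethnicity, and insurance status".
- Tests (Statistical analysis): "t-test comparisons between those referred and prescribed PrEP will be reported for continuous" variables. Wilcoxon, chi-square and Fisher tests follow, with no other groups named.
- Model (same paragraph): variables with bivariate p≤0.1 "will be included in multivariable logistic regression analyses. Model fit will be determined using Hosmer and Lemeshow tests". The model's outcome and comparison group are not written down.

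**SAP.** Paper 1, Preliminary Effectiveness, repeats the objective almost word for word. Its procedures are a frequency line that breaks off and a demographic report on those prescribed. No test, model, screen or comparison group is named. The Quantitative data list gives "Patient visits by intervention period; total n=4161" and "PrEP prescriptions per period; n=11". Items 3 and 4 list near-identical variables for all patients and for patients with a prescription. The study periods run from a pre-implementation stage (January to July 2023) through "PrEP4Her implementation July 2023 January 2024; Pilot January 2024-August 2024".

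**The concern.** There are two gaps.

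1. **The contrast.** Comparing referred with prescribed women conditions on having been referred or prescribed. It can describe follow-through after referral. It cannot show which of the women seen receive PrEP, which is the stated question. Because the groups are not said to be mutually exclusive, one woman could be in both. Two analysts could therefore report different comparisons under the same objective.

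2. **The model.** The SAP was started in September 2025, after the pilot, with the prescription count already known, but it is silent on the protocol's screened multivariable model. With 11 events, the screen would tend either to drop a modest association for a binary factor or to report it as a large one. A category with no prescription gives no finite odds ratio in ordinary logistic regression.

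At stake are the reported associations in Paper 1 and any use of them in planning the multi-site study.

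**Working it through.** The documents give no sample size, power or precision figure for this analysis, so there is no stated result to reproduce. The check asks what the protocol's method would do with the SAP's counts.

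**Inputs.** 11 prescriptions (SAP item 1b; item 7a also lists 11 patients). Four candidate factors (protocol). N = 4,241, from the SAP's table of PrEP indications (item 8). The share of women holding a binary factor is not given, so 20% to 50% is assumed. The site's overall 40% Black share (protocol B1) serves as one example.

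**Events per candidate parameter.** 11 / 4 = 2.75. This is an upper limit for the candidate set, since race or insurance with more than two levels adds parameters. The fitted model has more events per parameter if few factors pass the screen.

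**Screen, binary factor, 40% exposed** (1,696 of 4,241), prescribed versus not prescribed:

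- 7 of 11 exposed: OR = (7 × 2,541) / (4 × 1,689) = 2.63; p = 0.123 (Wald), 0.114 (likelihood ratio), 0.129 (Fisher). Dropped.
- 8 of 11 exposed: OR = (8 × 2,542) / (3 × 1,688) = 4.02; p = 0.040, 0.028, 0.033. Passes.

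The chance that 8 or more of 11 are exposed when the true OR is 2 (noncentral hypergeometric) is 0.232.

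**Other shares.** At these four shares the three tests give the same threshold:

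| Share exposed | Smallest passing OR above 1 | Chance a true OR of 2 passes |
|---|---|---|
| 20% | 3.35 | 0.287 |
| 30% | 2.81 | 0.395 |
| 40% | 4.02 | 0.232 |
| 50% | 4.52 | 0.233 |

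Between these points the threshold jumps, because only whole women can be counted, and the tests disagree. At 39%, for example, the likelihood ratio test passes from OR 2.74 and the Wald test from 4.19. In 1% steps from 20% to 50%, the smallest passing OR runs from 2.7 to 4.7 (likelihood ratio), 2.8 to 5.1 (Wald) and 2.8 to 5.3 (Fisher). Over all three tests, a true OR of 2 passes about 16% to 43% of the time.

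**Continuous factor (age).** The threshold is about exp(1.645 / √11) = 1.64 per SD. For a true OR of 2 per SD: ln 2 × √11 − 1.645 = 0.654, so it passes about 74% of the time. The screen is much less restrictive here.

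**Empty category.** With no association, the chance that none of the 11 falls in a category of share q is (1 − q)^11: 0.569 at q = 5% and 0.167 at q = 15%.

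**Hosmer-Lemeshow.** Ten groups would average 11 / 10 = 1.1 events each.

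**The case against.** The strongest reply is that context settles the comparison. The objective names prescription, the extract covers all women seen, a logistic model needs a binary outcome, and SAP items 3 and 4 set all patients beside those prescribed. On that reading one sentence is loosely worded. This makes prescribed versus not prescribed the likely intent, but neither document states it, the tests are tied in writing to the referred and prescribed groups, and item 3 as listed includes the 11 women.

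Second, the SAP's procedures look descriptive, so the model may have been dropped. A reader might infer that the trial will fit a multivariable model to 11 events. The documents do not support that: the SAP neither keeps nor withdraws the model, and its frequency line is unfinished. The figures above apply only if the model is run.

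Third, a reader might take an odds ratio of 4.0 as a fixed threshold. It belongs to a share of exactly 40%; at 38% the Wald and likelihood ratio threshold is 2.86. Only the range is safe. Likewise, 2.75 does not describe the fitted model: if a single one-parameter factor passes the screen, the figure is 11. Nor is the screened model the only inferential method on file, because the t, Wilcoxon, chi-square and Fisher tests are also specified.

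Finally, this is a secondary analysis in a one-arm pilot. That limits the consequence but does not remove the gap.

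**Conclusion.** The point holds. The only contrast written down does not answer the objective retained in the SAP, and the SAP leaves unresolved a screened model that 11 events support poorly. If that model is run, a binary factor passes only from an estimated odds ratio of about 2.7 to 5.3, a true odds ratio of 2 passes about 16% to 43% of the time, and a category held by 5% to 15% of women has no prescription with probability 57% to 17%.

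These figures assume 11 distinct women prescribed, N = 4,241, and shares that the documents do not give. The 11 covers all study periods, so a restriction to the pilot or to Black women could leave fewer events. Continuous age is less affected. The consequence is confined to the reported associations and does not reach the prescription count that defines Reach or the fidelity results. It should be fixed before Paper 1 is analysed.

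**What to change.** In the SAP:

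1. Replace the referred-versus-prescribed comparison, wherever the protocol's tests rely on it, with women prescribed PrEP versus women not prescribed PrEP. Limit both groups to women not known to be living with HIV and seen in the same named periods (stating whether pre-implementation counts), with one record per woman. Define *referred* and show referred women only as description.
2. Withdraw the p≤0.1 screen, the multivariable model and the Hosmer-Lemeshow test for this outcome.
3. Report age, race, ethnicity and insurance one at a time, with counts and Firth logistic regression with profile-likelihood 95% intervals, labelled exploratory and replacing the separate tests. Name one method only, because the choice matters: for 8 of 11 exposed at 40%, Firth gives OR 3.66 (1.13 to 14.8), while the exact interval is 0.96 to 23.5. State any factor dropped because it was not extracted for all women.

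If only description is intended, say so and reword the SAP sentence about association.

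**Cost.** SAP wording and some data work. The SAP's all-patient list lacks age, ethnicity and insurance, so these must be extracted or explicitly dropped, and visits must be collapsed to women. There will be no adjusted odds ratios, and intervals will be wide.

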**Procedures:**

- a. **Frequencies of PrEP prescriptions by**
- b. **Report demographics of patients prescribes PrEP**
- 3. **Adoption:** Defined as the proportion of key-stakeholders within our pilot site who were willing to initiate our implementation strategy.

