**Procedures:**

- a. **Number of providers/staff who attended PrEP4Her trainings**
- b. **Track clicks for asynchronous training attendance**
- c. **RedCap survey item for providers – Did you access these training materials to aid in the PrEP implementation at the GYN Continuity Clinic?**
- d. **Chart review – number of patients seen during pilot who receiving a sexual history screener.**
- 4. **Acceptability:** Extent to which key stakeholders, both provider delivering the intervention and Black cis-gender women receiving it, felt PrEP4Her was acceptable.

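### Adoption is defined as a proportion of pilot-site stakeholders, but the listed procedures supply no staff denominator and include a patient count in a different unit

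*Combined protocol and SAP*

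**What the plan says.** In the protocol's Adoption Outcome paragraph (Specific Aim 3, Procedures for Evaluating Proximal Implementation Outcomes), "we define adoption as the proportion of key-stakeholders within our pilot site who were willing to initiate our implementation strategy". The SAP (Paper 1, item 3) keeps this: "Defined as the proportion of key-stakeholders within our pilot site who were willing to initiate our implementation strategy".

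The protocol then lists four procedures:

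- Synchronous training: "we will document the number of providers and staff who attend meeting".
- Asynchronous training: "collecting para-data (to track clicks) on the number of providers and staff who visit the CFAR website and access training materials".
- A single REDCap item linked to the end of the training materials: "Did you access these training materials to aid in PrEP implementation at the UAB GYN Continuity Clinic"?
- Sexual history, by chart review: the "absolute number of patients seen during our pilot timeframe who had a sexual history taken".

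The SAP's procedures for adoption repeat all four, with the second shortened to "Track clicks for asynchronous training attendance". Under Quantitative data, item 5, the SAP lists "Sexual health pre-screener survey; n=1135". Items 1, 2 and 8 of the same list give 4161 visits, 4635 charts reviewed (6 missing) and 4241 women classified by PrEP indication.

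Neither document gives the number of eligible providers and staff at the pilot site, a rule for who counts as a stakeholder, a rule for what counts as willing to initiate, or an analysis for adoption.

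**The concern.** A proportion needs a numerator and a denominator in the same unit. Here the unit in the definition is a clinic stakeholder, yet no procedure refers to the full set of stakeholders, and one counts patients.

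Two practical problems follow. Click data record page activity: one person can generate several clicks, and the plan has no rule for identifying distinct people or for separating clinic staff from other visitors. Also, the sexual history screener is called universal in Table 4, with a dose of one brief screener at every visit. For such a component the informative quantity is coverage, which a bare count does not show.

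Adoption is one of the three RE-AIM dimensions that the proposal sets out to assess (section A5), and section C4 names low adoption as a threat to PrEP4Her. If the procedures are followed literally, Paper 1 will report numbers under the adoption label that are not the outcome it defines.

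**Working it through.** The plan states no adoption figure, target or sample-size basis, so there is nothing to reproduce. The check compares the definition with each procedure, then shows how far a count leaves the proportion open.

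**Step 1. Definition against procedures.** The definition requires stakeholders willing to initiate, divided by all key stakeholders at the site.

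| Procedure | Unit recorded | Denominator stated | Gives the defined proportion? |
|---|---|---|---|
| Synchronous training | Attendees | None | No; numerator only |
| Asynchronous training | Website clicks, read as staff | None; no unique-person rule | No |
| REDCap item | Individual answer about this clinic | Only those who reach the end of the materials | No; those who never opened them are not asked |
| Sexual history | Patients | None; stated as an absolute number | No; different unit |

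**Step 2. Is a staff denominator given elsewhere?** Table 2 names one for adoption, but it belongs to the Aim 1 survey of 250 Alabama practitioners. The 15–20 key informants under the Acceptability Outcome are an interview sample, not a list of clinic staff. So there is none for the pilot site.

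**Step 3. What a count of staff leaves open.** Both the attendance (12) and the roster sizes below are assumptions, since the documents give neither. Proportion = attendees / roster.

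- 12/15 = 80%
- 12/20 = 60%
- 12/30 = 40%
- 12/40 = 30%
- 12/60 = 20%

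Even with the roster known, a small clinic gives a wide interval: for 12/20 the Wilson 95% interval is 38.7% to 78.1%. The result should therefore carry an interval.

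**Step 4. What the patient count leaves open.** Numerator: 1135 pre-screeners (SAP item 5). Candidate denominators are from SAP items 1, 8 and 2.

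- 1135/4161 visits = 27.3%
- 1135/4241 women = 26.8%
- 1135/4635 charts = 24.5% (also 24.5% of 4629 after removing the 6 missing)

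These show only how a count becomes a rate. The SAP's study population runs from January 2023 to August 2024 and includes a pre-implementation stage, so the totals may cover months before the screener was in use. The SAP also does not label 1135 as the adoption count; that count is to come from chart review within the pilot. The three denominators are in different units (visits, women, charts), and the SAP does not say which applies.

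**The case against.** The strongest reply is that this is a missing specification in a descriptive outcome of a one-arm pilot, at a single clinic with one of its own physicians on the study team. Attendance over a staff list would give a proportion at once. Visit data for the pilot timeframe are already to be extracted (Reach Outcome, Procedures), and the SAP lists visits by period (item 1a) and the month and year in which screened participants were seen (item 5c). Screening is also examined under fidelity, where surveyed patients are asked whether a history was taken. All of this stands, and it is why the remedy is cheap. It does not remove the mismatch: no roster is mentioned, and the fidelity survey (242 responses in the SAP, from patients who took up a flyer) is self-reported and says nothing about the share of staff adopting.

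Several stronger readings are tempting but are not supported:

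- *Adoption can never be computed.* A roster would supply the denominator; the plan simply does not ask for one.
- *Every procedure is a bare count.* The REDCap item gives individual answers tied to this clinic, which partly addresses outside visitors to the website.
- *Summing the sources double-counts staff.* Neither document says they will be summed, and the two trainings are separate components that one person may properly complete.
- *Adoption decides whether the multi-site trial goes ahead.* Section C6 names feasibility, acceptability and preliminary efficacy.
- *Pilot screening coverage was about a quarter.* Step 4 cannot show this, because the periods may be mixed.
- *The counts have misled.* No adoption result is reported; this is a risk only.

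**Conclusion.** The concern holds as a mismatch between an outcome's definition and its measurement. Following the listed procedures would produce attendance numbers, click data, answers from people who finished the materials, and a patient count, but not the stakeholder proportion that both documents define.

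The size of the gap for staff is unknown: the 20% to 80% span rests wholly on assumed values and shows only that a count does not determine the proportion. The 24% to 27% screening figures rest on the SAP's own totals but are not pilot coverage unless numerator and denominator are shown to come from the same window. The point deserves correction before Paper 1 is analysed. It does not undermine the other outcomes.

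**What to change.** 1. **Stakeholder adoption.** Define the denominator as the roster of pilot-site providers and staff at the training date. Define the numerator as distinct people on that roster who completed training, taken from attendance records and, where the respondent can be identified, the REDCap item. State that completing training is the working definition of willing to initiate. Report n/N with an exact or Wilson interval. If attendance was kept only as a headcount, report it over the roster for that session and say that individuals could not be linked across trainings.
2. **Clicks.** Report them as a descriptive website metric, not as adoption.
3. **Screening coverage.** Report visits (or patients) screened divided by all eligible visits (or patients) in the pilot window, and by period, using SAP items 1a and 5c. Label this separately from stakeholder adoption. State which of 4161, 4241 or 4635 applies, its unit and its dates, and restrict it to the pilot window for the main figure.

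A provider-level screening rate should not be promised from SAP item 7. That item records the physician only for the 11 prescriptions, and Table 4 allows a medical assistant to do the screening.

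The cost is SAP wording, one staff roster and a small amount of extra tabulation. The SAP is dated September 2025, after the pilot ended, so the roster must be obtained retrospectively; no new patient data are needed.
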